7.4 Inclusion Criteria

In order to be eligible to participate in this study, each subject must meet all of the following criteria:

1. Subject has given written informed consent

2. Male or female, at least 18 years of age
3. Diagnosis and treatment of HF (regardless of left ventricular ejection fraction (LVEF)) for ≥ 3 months and NYHA Class III HF at time of Screening
4. Subjects should be on stable, optimally titrated medical therapy for at least 30 days, as recommended according to current American Heart Association (AHA)/American College of Cardiology (ACC) guidelines as standard-of-care for HF therapy in the United States, or current European Society of Cardiology (ESC) guidelines for HF treatment in Europe, with any intolerance documented.
5. HF related hospitalization, HF treatment in a hospital day-care setting, or urgent outpatient clinic HF visit for IV diuretics within 12 month (last hospitalization should be 30 days before Screening /Enrollment) **and/or** N-terminal pro-Brain Natriuretic Peptide (NT-proBNP) at time of Screening/ Enrollment defined as:
 - a. Subjects with LVEF $\leq 50\%$: NT-proBNP ≥ 1500 pg/mL.
 - b. Subjects with LVEF $> 50\%$: NT-proBNP ≥ 800 pg/mL.

Thresholds for NT-proBNP (for both LVEF $\leq 50\%$ and LVEF $> 50\%$) will be corrected for body mass index (BMI) using a 4% reduction per BMI unit over 25 kg/m²

6. Subjects should be on diuretic therapy
7. Subjects who are physically able to hold the myCordella™ Patient Reader unit (approximate weight 1.3lb) against the ventral thoracic surface for up to 2 minutes per day while in a seated position, as well as dock and undock the myCordella™ Patient Reader
8. Subjects with sufficient eyesight, hearing, and mental capacity to respond to the myCordella™ Patient Reader's audio/visual cues and operate the myCordella™ Patient Reader
9. Subject has sufficient Cellular and/ or Wi- Fi Internet coverage at home
10. Subject agrees to return to the treating Investigator for all scheduled follow up visits and can return to the hospital for follow up

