8.1.6 Cardiac/Medical and Surgical History

Medical and surgical history, including cardiac history, will be obtained at Screening and updated at the Cordella PA Sensor Implant Visit prior to the implant procedure as follows:

- General medical history
- Primary cardiac diagnosis (ischemic cardiomyopathy/ nonischemic cardiomyopathy)
- Previous cardiac history incl.:
 - Coronary Artery Bypass Grafting (CABG)
 - Percutaneous coronary intervention (PCI)
 - Hypertension
 - Ventricular Tachycardia
 - Atrial Fibrillation
 - ICD / CRT
- Duration of Heart Failure/ NYHA class
- Cardiopulmonary Exercise Testing (CPX) Results (if available)
- Number of hospitalizations in past year for cardiac reasons and HF
- Smoking, Alcohol, Drug Use

With co-morbidities to be identified as:

- Diabetes (diet, oral, insulin)
- COPD
- Chronic Kidney Disease
- Carotid artery disease, Peripheral vascular disease

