9 ADVERSE EVENTS

From the time of enrollment, at each evaluation of a subject enrolled in the trial, the investigator or site staff determines whether any adverse events (AE) have occurred and determines their relationship to the study devices or procedures. All adverse events, study device malfunctions and other product issues must be recorded in the appropriate eCRF section(s).

Safety will be assessed throughout the study by the frequency of Adverse Events (AEs), pressure sensor failure rate, and device/system-related complications by relationship to the device and severity. Additional emphasis on safety for the primary safety endpoint will be placed through 6 month following the Cordella PA Sensor Implant procedure to capture any adverse events associated with use of the Cordella PA Sensor.

Adverse events may be volunteered spontaneously by the subject, or discovered as a result of general, non-leading questioning. If it is determined that an AE has occurred, the investigator should obtain all the information required to complete the AE page of the eCRF, in accordance with the guidelines that accompany it. The investigator must submit to sponsor (or designee) any UADEs, and SAEs occurring during the study within 24 hours after being notified of the event and provides additional information, if required by Endotronic.

All AEs must be followed until resolution, until the condition stabilizes, until the event is otherwise explained or is judged by the investigator to be no longer clinically significant, or until the subject is lost to follow-up. The investigator is responsible for ensuring that follow-up includes any supplemental investigations necessary to elucidate as completely as practical the nature and/or causality of the AE. This may include additional laboratory tests or investigations, histopathological examinations, or consultation with other health care professionals.

Investigators are not obligated to actively seek AEs in former study participants. However, if the investigator learns of any SAE, including a death, at any time after a subject has been discharged from the study, and he/she considers the event reasonably related to the investigational product or study participation, the investigator should promptly notify Endotronic.

All AEs will be collected until a subject's participation in the trial is considered complete.

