Cardiovascular death includes death resulting from an acute myocardial infarction (MI), sudden cardiac death, death due to HF, death due to stroke, death due to CV procedures, death due to CV hemorrhage, and death due to other CV causes.

Non-cardiovascular death

Any death in which the primary cause of death is clearly related to another condition (e.g. trauma, cancer, suicide).

DEVICE / SYSTEM-RELATED COMPLICATION

A Device /system related complication is an adverse event that is, or is possibly, related to the system (wireless pressure sensor or external electronics) and at least one the following:

- is treated with invasive means (other than intramuscular medication or a right heart catheterization with a Swan-Ganz measurement which is used for diagnostic purposes)
- results in the death of the subject
- results in the explant of the device

HEART FAILURE (HF)

A HF Event includes hospitalization for HF and may include urgent, unscheduled outpatient office/practice or Emergency Department (ED) visits.

- A HF Hospitalization is defined as an event in which the patient is admitted to the hospital with a primary diagnosis of HF, the length of stay is at least 24 h, the patient exhibits new or worsening symptoms of HF on presentation, has objective evidence of new or worsening HF, and receives initiation or intensification of treatment specifically for HF.
- An Urgent HF Visit is defined as an event in which the patient has an urgent, unscheduled office/practice or ED visit for a primary diagnosis of HF but is not admitted to the hospital and exhibits new or worsening symptoms of HF on presentation, has objective evidence of new or worsening HF, and receives initiation or intensification of treatment specifically for HF. Note that changes to oral diuretic therapy do not qualify as initiation or intensification of treatment.

HEMOPTYSIS

Spitting up blood or blood-tinged sputum from the respiratory tract. Hemoptysis occurs when tiny blood vessels that line the lung airways are broken.

MYOCARDIAL INFARCTION (MI)

Peri-procedural MI (≤72 h after the index procedure)

- New ischemic symptoms (e.g. chest pain or shortness of breath), or new ischemic signs (e.g. ventricular arrhythmias, new or worsening HF, new ST-segment changes, hemodynamic instability, new pathological Q-waves in at least two contiguous leads, imaging evidence of new loss of viable myocardium or new wall motion abnormality).

AND

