7.1. Primary Efficacy Endpoint and Analysis

The primary efficacy endpoint is the 6 month incidence of HF related hospitalizations (HFH) or all-cause mortality.

The information on mortality will be used as collected on the CRF, AE page with AE outcome = 'Death' or Study completion page with primary reason for discontinuation = 'Death'.

The information on HF hospitalizations will be used as collected on the CRF, Hospitalization page, only hospitalizations due to heart failure and stay at least 24 h will be considered as HF related hospitalizations

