7.1.4. Incidence of HF Hospitalizations or all-cause mortality at 12 months

The mathematical statement of the null and alternative hypothesis for the first secondary efficacy is as follows:

$$H_0: r_{12} \geq PG_{12}$$

$$H_A: r_{12} < PG_{12}$$

where r_{12} is the 12 month rate of secondary endpoint events and PG_{12} is the performance goal. A value of 0.70 will be used for the goal. The null hypothesis will be rejected if the upper confidence bound for the rate is less than the performance goal, or equivalently, that the corresponding p-value from the hypothesis test is less than 0.025. An observed value of less than 0.59 and rejection of the null will indicate that the observed rate is statistically less than the performance goal, indicating clinically acceptable results.

Analysis will be based on a Poisson regression approach for the number of events, with the log follow-up time as an offset term. Sensitivity analyses using a negative binomial approach to capture within-subject correlation will be performed.

12 month incidence of HF related hospitalizations (HFH) or all-cause mortality will be analyzed on the mITT, PP and Cohort #1 population in a similar manner to the primary efficacy endpoint.

7.1.5. Number of HF Hospitalizations at 6 and 12 months post-implant compared to the number of HF Hospitalizations in the 6 and 12 months prior to implant

Heart Failure hospitalizations will be summarized by cohort presenting number of subjects without any hospitalizations at 6 and 12 months post-implant visit, number of subjects with any hospitalizations at 6 and 12 months post-implant visit, number of hospitalizations per subject at 6 and 12 months post-implant visit, and mean number of hospitalizations per subjects at 6 and 12 months post-implant visit. Similar presentation will be done based on the CRF information on the number of hospitalizations in the 6 and 12 months prior to implant. 95 % Clopper-Pearson confidence interval (CI) will be provided in addition for the frequencies as applicable. In additional, Wilcoxon rank sum tests will be performed to compare the number of hospitalizations per subject at 12 months post-implant visit with 12 months prior-implant visit, and compare the number of hospitalizations per subject at 6 months post-implant visit with 6 months prior-implant visit.

The 6 and 12 months timepoint is independently of visit information and is calculated as:

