9. PRESSURE SENSOR FAILURE
10. PULMONARY EMBOLISM
11. PULMONARY OCCLUSION
12. RENAL DYSFUNCTION classified as Acute renal dysfunction or Chronic renal dysfunction
13. STROKE (Non-Fatal) AND TRANS ISCHEMIC ATTACK (TIA) classified as Stroke or TIA
STROKE CLASSIFICATION as Ischemic, Hemorrhagic or undetermined
STROKE DEFINITION as Disabling stroke or Non-disabling stroke
14. VASCULAR ACCESS SITE AND ACCESS-RELATED COMPLICATIONS classified as Major vascular complications or Minor vascular complications
15. VESSEL TRAUMA classified as Blunt injury or Penetrating injury
16. OTHER <specify>

All SAEs and some selected AEs will be sent for adjudication.

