	14.2.2.1.11a	SAS-Output: 12-month incidence of HF hospitalizations (HFH) or all-cause mortalities from CEC adjudication results	Cohort #1 Population
	14.2.2.1.12	Sensitivity Analysis - 12-month incidence of HF hospitalizations (HFH) or all-cause mortalities from CEC adjudication results using negative binomial regression model	mITT Population
	14.2.2.1.12a	SAS-Output: Sensitivity Analysis - 12-month incidence of HF hospitalizations (HFH) or all-cause mortalities from CEC adjudication results using negative binomial regression model	mITT Population
14.2.2.2		Number of HF Hospitalizations at 6 and 12 months post-implant compared to the number of HF Hospitalizations in the 6 and 12 months prior to implant	
	14.2.2.2.1	Number of pre and post implant HF hospitalizations at 6 and 12 months post implant visit	mITT Population
	14.2.2.2.2	Number of pre and post implant HF hospitalizations at 6 and 12 months post implant visit, stratified by sex	mITT Population
	14.2.2.2.3	Number of pre and post implant HF hospitalizations at 6 and 12 months post implant visit, stratified by heart failure ejection fraction	mITT Population
	14.2.2.2.4	Number of pre and post implant HF hospitalizations at 6 and 12 months post implant visit	Per Protocol Population
	14.2.2.2.5	Number of pre and post implant HF hospitalizations at 6 and 12 months post implant visit	Cohort #1 Population
	14.2.2.2.6	Number of pre and post implant HF hospitalizations at 6 and 12 months post implant visit from CEC adjudication results	mITT Population
	14.2.2.2.7	Number of pre and post implant HF hospitalizations at 6 and 12 months post implant visit from CEC adjudication results, stratified by sex	mITT Population
	14.2.2.2.8	Number of pre and post implant HF hospitalizations at 6 and 12 months post implant visit from CEC adjudication results, stratified by heart failure ejection fraction	mITT Population
	14.2.2.2.9	Number of pre and post implant HF hospitalizations at 6 and 12 months post implant visit from CEC adjudication results	Per Protocol Population

This document is confidential.

Header	Table Number	Name	Analysis Set
	14.2.2.2.10	Number of pre and post implant HF hospitalizations at 6 and 12 months post implant visit from CEC adjudication results	Cohort #1 Population
14.2.2.3		Comparison of the number of HF Hospitalizations or Emergency Department/ Hospital Outpatient IV diuretic visits of Cohort #1 and Cohort #2 + Cohort #3 at 6 and 12 months post implant	

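### The 'before' window of the pre/post HF hospitalisation endpoint overlaps the entry criterion, so a device with no effect could show a sizeable 12-month fall, and the CEC version promises adjudicated pre-implant counts that the documents give no way to produce

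*SAP*

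**What the plan says.** SAP 7.1.5 summarises post-implant HF hospitalisations at 6 and 12 months and then adds: "Similar presentation will be done based on the CRF information on the number of hospitalizations in the 6 and 12 months prior to implant". The windows run 180 and 365 days either side of implant, and a Wilcoxon rank sum test compares the two counts.

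- **Definition.** SAP 7.1, written for the primary endpoint's CRF Hospitalization page, says "only hospitalizations due to heart failure and stay at least 24 h will be considered as HF related hospitalizations". Protocol 14.6 defines an HF hospitalisation in general terms: "the length of stay is at least 24 h, the patient exhibits new or worsening symptoms of HF on presentation", with further conditions. Section 7.1.5 repeats neither.
- **History item.** Protocol 8.1.6 lists "Number of hospitalizations in past year for cardiac reasons and HF". No stay-length rule is attached to it.
- **Entry.** Inclusion criterion 5 (Protocol 7.4) accepts an HF hospitalisation, day-care HF treatment or "urgent outpatient clinic HF visit for IV diuretics within 12 month", and/or raised NT-proBNP. The last hospitalisation should be 30 days before screening.
- **CEC.** Tables 14.2.2.2.6 to 14.2.2.2.10 in the SAP index are titled "Number of pre and post implant HF hospitalizations at 6 and 12 months post implant visit from CEC adjudication results". SAP 8.3.3 says "All SAEs and some selected AEs will be sent for adjudication". Protocol Section 9 starts adverse event collection thus: "From the time of enrollment, at each evaluation of a subject enrolled in the trial".
- **Status.** Only the 12-month composite sits behind the primary endpoint in the gatekeeping. All other secondary p-values are nominal (Protocol 10.4, SAP 2.4.2).

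**The concern.** A subject admitted to the trial because of a recent hospitalisation carries that event into the 'before' count. The 'after' count has no such selection. Even with an unchanged underlying rate, the first tends to exceed the second, and nothing in 7.1.5 addresses this.

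This is a named secondary endpoint in a single-arm study. Protocol 1.2 cites a 58% one-year pre/post fall from an earlier post-approval study as evidence of benefit, so a fall here could be read the same way.

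The CEC tables raise a second problem. If the 'before' side has no adjudicated data, the comparison sets either unadjudicated or near-empty counts against adjudicated ones. The third problem is silence: the reader cannot tell whether 'before' and 'after' events meet the same definition.

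**Working it through.** The plan states no expected reduction or power for this endpoint, so there is no figure of its own to reproduce.

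**Inputs from the documents:** windows of ±180 and ±365 days from implant; 12-month look-back from screening; 30-day gap before screening.

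**Assumed:** 14 days from screening to implant; no admissions in the resulting 44 days before implant; one constant rate per subject before and after implant, gamma distributed with mean m = 0.3, 0.4 or 0.5 per year and shape k = 0.5, 1 or 2; a share f entering with at least one HF hospitalisation in the look-back, and the rest, from the same rate distribution, with none.

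**Overlap.** The look-back covers days 44 to 379 before implant (335 days). The 12-month window holds 321 of these (321/335 = 96%) and the 6-month window 136 (136/335 = 41%).

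**Formulas**, with T = 335/365:
- Probability of no admission in the look-back: P0 = (1 + mT/k)^(−k)
- Mean rate given none: E0 = m/(1 + mT/k)
- Mean rate given at least one: E1 = (m − P0·E0)/(1 − P0)
- 'Before' mean: f·m·(321/365)/(1 − P0) at 12 months; replace 321 by 136 at 6 months
- 'After' mean, no device effect: f·E1 + (1 − f)·E0 at 12 months; multiply by 180/365 at 6 months

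**Worked case** (m = 0.5, k = 1, f = 0.7): P0 = 1/1.4589 = 0.685; E0 = 0.343; E1 = (0.5 − 0.685 × 0.343)/0.315 = 0.843.
- 12 months: before 0.7 × 0.5 × 0.879/0.315 = 0.98; after 0.7 × 0.843 + 0.3 × 0.343 = 0.69; fall 29%.
- 6 months: before 0.41; after 0.34; fall 18%.

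**Range over all nine combinations of m and k:**

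| Entering by HF hospitalisation | 12-month fall | 6-month fall |
|---|---|---|
| 70% | 22–54% | 9–46% |
| 40% | 0–29% | −16% to +18% |

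The largest falls occur at m = 0.3, k = 2. The smallest occur at m = 0.5, with k = 0.5 for f = 0.7 and k = 2 for f = 0.4. A negative value is an apparent rise.

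**Second check, by simulation.** Here m was calibrated so that the post-implant 12-month rate was 0.45 or 0.60, close to the HF hospitalisation rates of 0.431 to 0.60 in SAP 2.4.2. The no-effect fall at 12 months was 52–62% (f = 1.0), 41–54% (0.8), 25–41% (0.6) and −10% to +19% (0.4). At 6 months it was 44–56%, 31–47%, 12–32% and −28% to +6%. With n = 406 and k = 1, the rank sum test at two-sided 0.05 falsely showed a 12-month reduction in essentially every run when f was 0.6 or more, and in 0–51% of runs at f = 0.4.

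**CEC tables.** Set side by side: the titles cover pre and post; only SAEs and selected AEs are sent for adjudication; AEs begin at enrolment. Of the year before implant, only the short stretch between enrolment and implant can yield adjudicated events.

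**The case against.** Several stronger readings are tempting, and the documents do not support them.

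- **That the 24-hour rule applies only after implant.** Section 7.1.5 states it for neither side, and the Protocol 14.6 definition is not limited to post-implant events. The history item may not even be the source: a single past-year total cannot give a 6-month count, so the CRF may hold dated admissions. What stands is that the 'before' rule is unstated.
- **That the whole endpoint is adjudicated on one side only.** The main table uses CRF data on both sides, so the CEC problem is confined to five tables. The CEC charter is not available and might describe a process. Nothing shows in which direction adjudication would move the counts.
- **That a large fall is certain.** Criterion 5 can be met without any hospitalisation, and the 30-day gap works in the opposite direction. Protocol 7.1 and SAP 2.3 describe raised NT-proBNP together with a prior event, but that event need not be an admission either.
- **That every hospitalisation entrant has a 'before' count of at least one.** This is nearly so at 12 months but not at 6. A single admission spread evenly over the look-back falls in the 6-month window only 41% of the time.
- **That nothing in the plan gauges the artefact.** Table 14.2.2.2.5 gives the same comparison for Cohort #1, the former control arm. It is imperfect: up to 85 subjects, some crossed over early.

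The endpoint is also nominal and outside the gatekeeping, which limits the consequence. None of this removes the window overlap.

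**Conclusion.** The concern holds in conditional form. At 12 months a device with no effect could show a sizeable fall, and would if most subjects entered through an HF hospitalisation: about 22–54% at 70% entry, against about 0–29% at 40%. At 6 months the artefact is smaller and can reverse. These sizes rest on the assumed rates, dispersion, 14-day lag and common rate distribution; the entry mix, which drives them most, is not in the documents. Deaths and withdrawals were not modelled. Section 7.1.5 states no exposure adjustment, so they would lower the post-implant count further.

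The five CEC tables cannot be produced as titled from the processes described, and the definition for 'before' events needs stating. Study success is not affected. The change should be made because the endpoint invites a causal reading that its design cannot carry.

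**What to change.** 1. Drop the CEC version of the pre/post comparison (Tables 14.2.2.2.6–10), or retitle those tables and limit them to post-implant counts.
2. State in 7.1.5 that the Protocol 14.6 definition applies to both sides wherever stay length is available, and report how many 'before' events lack it.
3. Report the result by entry route: HF hospitalisation, versus IV-diuretic or day-care visit or NT-proBNP only. Place the planned Cohort #1 result beside it as an imperfect gauge of regression to the mean.
4. Optionally add the 'before' count without the one qualifying hospitalisation, labelled as an over-correcting sensitivity bound and kept out of any headline range. It over-corrects because, in the worked case, removing one event from each hospitalisation entrant with a 12-month 'before' event leaves about 0.43 per such entrant, below their underlying rate of 0.84.
5. State that the pre/post fall is descriptive and does not estimate the device effect.

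The cost is SAP wording, a few more tables and a less favourable reading of the reduction. No clinical procedure changes.
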